8.3 Analysis Populations

The population of "all enrolled subjects" consists of all those screened subjects who meet the requirements for study participation and are entered in the Baseline period of the study. The population of "all randomized subjects" consists of all those enrolled subjects who complete the Baseline Period, meet the inclusion/exclusion criteria and are randomized.

Safety Population: will include all subjects who received at least 1 dose of study drug and had at least one post-baseline safety assessment.

Full Analysis Set (FAS): will include all screened subjects who received at least 1 dose of study drug and have completed baseline and at least 1 valid post-randomization assessment of frequency of IA behaviors based on IA diary entry.

Per-Protocol (PP) Population: will include all subjects who completed Treatment Phase and did not have major protocol deviations (as defined in the SAP).

PK population: will include all subjects in the safety population who have received at least 1 dose of study drug and had one PK sample drawn which had quantifiable concentration for molindone.

The safety, psychometric, FAS, PP, and PK populations are based on randomized treatment received.

8.4 Demographics

Demographic variables include age, sex, ethnicity, race, height, weight, and medical history at Screening. Tabular summaries of the demographic/baseline variables will be presented for the safety, psychometric, FAS, and PP populations, except for medical history, which will be summarized for the safety population.

8.5 Subject Disposition

The number and percentage of subjects who completed and discontinued from the study will be summarized in each of the following categories:

- Subjects in the randomized population
- Subjects in the FAS population
- Subjects treated (safety population)
- Subjects in the PP study population

The reasons for study discontinuation may include one of the following:

• Subject withdrew consent

- Lost to follow-up
- Administrative reason
- Adverse event
- Investigator decision
- Failure to follow required study procedures
- Other

Only one reason for study discontinuation will be recorded for each subject.

8.6 **Protocol Deviations**

Protocol deviations will be presented in listings. If applicable, the number and percent of subjects within each type of protocol deviation will be presented using discrete summary statistics. Protocol deviations may include, but are not limited to:

- Non-compliance with any scheduled study visit
- Non-compliance with study treatment
- Disallowed concomitant medications
- Non-compliance with study inclusion or exclusion criteria
- Non-compliance with study assessment procedures

8.7 Study Medication Exposure and Compliance

Duration of exposure is defined as the total number of days a subject is exposed to study treatment. This will be calculated for each subject by taking the difference between the date of last dose *minus* the date of the first dose, *plus* 1 (date of last dose – date of first dose +1).

Duration of Treatment exposure will also be summarized using descriptive statistics (n, mean, SD, median, minimum, and maximum).

Percent of study drug compliance will be calculated as:

 $\{(D-R)/T^*(D_L-D_F+1)\}^*100$, where D=number of tablets dispensed, R= number of tablets returned, T= number of tablets administered, D_L = date of last visit (dose) and D_F = date of first visit (dose)

The number of tablets (T) taken each day may vary during the flexible Maintenance period: during the first week of maintenance a total of 6 tablets per day will be taken, whereas during week 2 and 3 of maintenance, the number of tablets taken will be between 4 and 6 depending upon the dose.

The study medication compliance will be summarized by compliance category (<80%, 80-120%, and >120%) and number of subjects in each compliance category. Study medication

This document is confidential. It contains proprietary information of Supernus[®] Pharmaceuticals, Inc. Any viewing or disclosure of such information that is not authorized in writing by the Sponsor is strictly prohibited. Such information may be used solely for the purpose of reviewing or performing this study.

compliance will also be summarized as a continuous variable using descriptive statistics (n, mean, standard deviation, median, minimum, and maximum).

Summaries of treatment compliance and exposure will be presented separately for the Titration period, Maintenance period and combined Titration and Maintenance periods.

9. EFFICACY ANALYSES

9.1 Primary Efficacy Analysis

The primary efficacy analysis is the percent change (PCH_T) in the frequency (unweighted score) of IA behaviors per 7 days in the Treatment Phase (titration + maintenance) relative to the Baseline period calculated over the number of days with non-missing IA diary data. The frequency of the IA behaviors per 7 days is the sum of the scores for all the events collected in a given period of sequential days, adjusted per 7 days.

The primary efficacy endpoint PCH_T will be calculated by $PCH_T = 100^*(T - B)/B$, where T and B are IA behavior frequencies per 7 days during the Treatment Phase and Baseline period, respectively. The IA behavior frequency per 7 days is defined as (SUM/DAY) x 7, where SUM is the sum of the IA behaviors reported in the subject IA diary, and DAY is the number of days with non-missing IA frequency data in the subject IA diary during the specified study period.

Let μ_1 , and μ_2 represent the median percent change in the frequency of IA behaviors per 7 days in the Treatment Phase, relative to the Baseline period in the FAS population for subjects treated with placebo and SPN-810 treatment, respectively. The null (H₀) and the alternative (H_a) hypotheses are as in the following:

H₀: $\mu_2 = \mu_1$, [there is no difference between the median of the SPN-810 treatment group and the median of placebo group] vs. H_a: $\mu_2 \neq \mu_1$, [there is a difference between the median of the SPN-810 treatment group and the median of placebo].

To test the above hypothesis, the primary efficacy analysis will be performed using the Wilcoxon rank-sum test to compare the median of SPN-810 with the median of the Placebo. The Hodges-Lehmann estimate of the difference (SPN-810 minus placebo) and the associated 95% confidence interval (CI) around the difference will be calculated.

When the median PCH_T from subjects in SPN-810 treatment group is significantly different from the placebo, further exploratory testing may be performed between other doses (45mg and 54mg) and placebo depending on the available sample size at each dose level.

9.2 Secondary Efficacy Analyses

9.2.1 Key secondary endpoints are:

1. Change from Visit 3 to Visit 7 in the Investigator-rated CGI-S score

- 2. Change from Visit 3 to Visit 7 in R-MOAS score
- 3. R-MOAS remission rate at Visit 7

9.2.2 Additional secondary endpoints:

- 1. Actual Investigator CGI-I score at Visit 7 and change from Visit 4
- 2. Actual Caregiver CGI-I score at Visit 7 and change from Visit 4
- 3. Change from Visit 3 to Visit 7 in the Caregiver-rated CGI-S score
- 4. Change from Visit 3 to Visit 7 in the SNAP-IV ADHD scores in:
 - a. Inattention ratings
 - b. Hyperactivity/Impulsivity ratings
 - c. ODD ratings
 - d. Combined scale ratings
- 5. Change from Visit 3 to Visit 7 in the CHQ-PF28 score
- 6. Change from Visit 3 to Visit 7 in the SIPA scores in:
 - a. Adolescents domain
 - b. Parent domain
 - c. Adolescents-Parents Relationship domain
 - d. Life Stressor domain

Each of the secondary endpoints will be analyzed using a Mixed-Effect Model for Repeated Measure (MMRM). MMRM assumes missing data as Missing at Random. The model includes treatment, visit, and interaction between treatment and visit as fixed factors, baseline as covariate. The model parameters will be estimated using restricted maximum likelihood method with unstructured variance-covariance matrix and Kenward-Roger approximation to estimate denominator degrees of freedom. The between-group comparison will be performed using the simple contrast at the respective visits. The least squares mean of the treatment group, the difference in the least squares mean (SPN-810 minus placebo), and the 2-sided 95% CI for the difference will be obtained.

To preserve the overall type I error rate at 0.05 for the secondary endpoints, only SPN-810 treatment group is significantly different from placebo for the primary endpoint will be tested for secondary endpoints.

The ordering of the three (3) key secondary endpoints from first to be tested to third is: Investigator-completed Clinical Global Impression – Severity Scale (CGI-S) (Endpoint 1); Retrospective Modified Aggression Scale (R-MOAS)(Endpoint 2); Retrospective Modified Aggression (R-MOAS) remission (Endpoint 3).

The ordering for the additional six (6) secondary endpoints from the first to the sixth is: Investigator-completed Clinical Global Impression – Improvement Scale (CGI-I)(Endpoint 1); Caregiver-completed Clinical Global Impression – Improvement Scale (CGI-I)(Endpoint 2); Caregiver-completed Clinical Global Impression – Severity Scale (CGI-S)(Endpoint 3);SNAP-IV

Rating Scale (Endpoint 4); Child Health Questionnaire (CHQ-PF28) (Endpoint 5) and SIPA Rating scale (Endpoint 6).

9.2.3 Sensitivity Analysis

The purpose of the sensitivity analysis is to see whether different methods of handling missing data provide consistent and similar results for the primary efficacy analysis. To this end, the following sensitivity analysis will be considered:

- 1. Multiple imputation under MAR
- 2. Placebo-based imputation under MNAR
- 3. Percent change (PCH_M) in the frequency of IA behaviors per 7 days in the Maintenance period relative to the Baseline period calculated over the number of days with non-missing IA diary data.

9.2.3.1 Multiple imputation under Missing at Random (MAR)

The multiple imputation (MI) method assumes that the missing data are missing at random (MAR), that is, the probability that an observation is missing may depend on the observed values but not the missing values. For example, if a subject's Diary values are available on Day 1 and Day 2 but missing on Day 3, then the missing value on Day 3 is related to the non-missing value on Day 1 and Day 2.

MI is implemented using the following three steps.

- 1. SAS PROC MI is applied with input dataset containing some missing values for all days during the titration and maintenance period to create 100 datasets. The data sets will include separate columns for the frequency of incidences during each day starting from baseline. The Markov Chain Monte Carlo (MCMC) method will be used to complete the missingness pattern to a monotone pattern separately by treatment arm. The monotone patterns will be achieved by applying sequential imputation based on Bayesian regression with the treatment arm included as a covariate. All copies contain identical values of the non-missing data items, but different values imputed for missing values.
- 2. For each of these MI data sets, the percent change will be computed as in the observed data set and the primary analysis based on the Wilcoxon rank-sum test will be conducted and asymptotic 95% confidence intervals will be constructed.
- 3. To produce a single confidence interval for each dose placebo comparison (e.g., Dose 1 versus placebo), PROC MIANALYZE will be used and Rubin's combination rules will be applied to the treatment effect estimates and associated asymptotic standard errors from the MI data sets. The treatment effect estimates will be defined as the midpoints

This document is confidential. It contains proprietary information of Supernus[®] Pharmaceuticals, Inc. Any viewing or disclosure of such information that is not authorized in writing by the Sponsor is strictly prohibited. Such information may be used solely for the purpose of reviewing or performing this study.

Supernus®	Pharmaceuticals,	Inc
810P503		

CONFIDENTIAL Version 3

of the asymptotic confidence intervals and the standard errors will be defined as the asymptotic standard errors (based on the width of the associated 95% confidence intervals) from the Hodges-Lehmann estimate of the individual datasets (Rubin 1987).

9.2.3.2 Multiple imputation under Missing Not at Random (MNAR)

This approach can be labeled "worst-case" sensitivity analyses as it assumes that after discontinuation subjects from the dosing arms would adopt the outcome model estimated from the placebo arm. To generate missing values from this "placebo-based" imputation model, PROC MI with the MNAR statement (available in SAS 9.3 and later versions) will be used or, alternatively, SAS macros available at the DIA Missing Data Working Group site (Ratitch et al., 2013; Ayele et al., 2014) can be used.

9.2.3.3 Per Protocol Analysis

This analysis will be conducted by repeating the primary analysis on the per protocol population.

9.3 Sample Size and Power Consideration

Assuming a mean difference of 15 between SPN-810 dose group and placebo with a common standard deviation of 35, a sample of 93 subjects per arm will yield 80 % power to detect a non-zero difference between the median of SPN-810 treatment group and the placebo group using the Wilcoxon rank-sum test with a 2-sided significance level α =0.05.

It is assumed that approximately 20% subjects will dropout before the completion of the study and hence, an adjusted total of 186 subjects will be randomized in a 1:1 ratio to obtain approximately 150 subjects at the completion of the study.

Sample size may be recalculated based on the effect size of the ongoing 810P301 and 810P302 studies.

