## **4.2** Sample Size and Power Consideration

Assuming a mean difference of 15 between SPN-810 dose group and placebo with a common standard deviation of 35, a sample of 93 subjects per arm will yield 80 % power to detect a non-zero difference between the median of SPN-810 treatment group and the placebo group using the Wilcoxon rank-sum test with a 2-sided significance level  $\alpha$ =0.05.

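### The total of 186 described as adjusted for 20% dropout is the unadjusted 2 × 93; about 150 contributing subjects would give about 71–72% power, not 80%

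*Protocol*

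**What the plan says.** Protocol 9.3 gives the design assumptions: "Assuming a mean difference of 15 between SPN-810 dose group and placebo", "with a common standard deviation of 35", and a Wilcoxon rank-sum test at a "2-sided significance level α =0.05". From these it states that "a sample of 93 subjects per arm will yield 80 % power to detect a non-zero difference".

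The next paragraph adds the loss assumption, "It is assumed that approximately 20% subjects will dropout before the completion of the study", and draws from it that "an adjusted total of 186 subjects will be randomized in a 1:1 ratio to obtain approximately 150 subjects at the completion of the study". The Synopsis has the same two paragraphs. Protocol 4.2 and 5.1 confirm that 93 per arm is the number randomized, and Protocol 5.7 says that withdrawn subjects are not replaced.

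SAP 4.2 repeats that "a sample of 93 subjects per arm will yield 80 % power" on the same assumptions. It mentions neither dropout nor the figure of 150.

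**The concern.** The number that is said to give 80% power and the number that is said to have been enlarged for dropout are the same. If 93 per arm is what the test needs, then 186 randomized with a fifth lost leaves fewer than the test needs. If about 150 completers are enough, then the 80% attached to 93 per arm cannot describe them. The three statements (80% power, 20% loss, about 150 remaining) cannot all belong to one calculation.

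At stake is a protection that the plan claims and does not have. A reader of 9.3 would believe that 80% power survives the expected dropout. A reader of SAP 4.2 alone would not learn that any dropout was expected.

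**Working it through.** **Inputs, all from Protocol 9.3:** difference 15; common SD 35; Wilcoxon rank-sum test; two-sided α = 0.05; target power 80%; dropout 20%; 186 randomized 1:1.

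**1. Reproduce the plan's 93 per arm.** For normal data with a shift, Noether's formula uses the probability that a subject in one arm scores above a subject in the other:

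- p = Φ(15 / (35 × √2)) = 0.6191
- N = (1.960 + 0.842)² / (12 × 0.25 × (p − 0.5)²) = 184.5 in total, or 92.3 per arm, rounded up to **93**

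Power is 79.9% at 92 per arm and 80.3% at 93, so 93 is the first size to reach 80%. It is the number to be *analysed* and holds no reserve.

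**2. Apply the stated dropout.**

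- Before inflation: 2 × 93 = 186
- With 20% loss allowed for: 93 / (1 − 0.20) = 116.25, so 117 per arm, 234 in total; 234 × 0.80 = 187.2, or 93.6 per arm, remain
- Shortfall of the plan's total: 234 − 186 = 48
- The cruder multiplication 93 × 1.20 = 111.6, so 112 per arm (224 in total), also exceeds 186
- Without inflation: 186 × 0.80 = 148.8, which matches the plan's figure of about 150, or 74 to 75 per arm

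**3. Power at the sizes in question.** Noether power = Φ(√(12 × 0.25 × N) × (p − 0.5) − 1.960):

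- N = 186: Φ(23.62 × 0.1191 − 1.960) = Φ(0.853) = 80.3%
- N = 150: Φ(21.21 × 0.1191 − 1.960) = Φ(0.566) = 71.4%

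| Method | 93 per arm | 75 per arm | 74 per arm |
|---|---|---|---|
| Noether | 80.3% | 71.4% | 70.9% |
| Simulation, normal data (20,000 and 40,000 trials) | 80.3%, 80.9% | 72.1%, 71.8% | 71.1%, 71.4% |
| Noncentral t, n scaled by 3/π | 81.1% | 72.1% | 71.6% |
| Normal approximation, n scaled by 3/π | 81.5% | 72.7% | 72.2% |

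The loss from 93 to 75 per arm is about 8 to 9 points by every method.

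**4. Try the other reading.** Suppose 150 was the base and 186 its inflated form: 150 / 0.80 = 187.5, close to 186. The dropout arithmetic then works, but 75 per arm gives at most 72.7%, so the stated 80% fails.

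**5. If dropouts stay in the analysis with a weaker effect.** The documents give no figure for this, so the following is an assumption shown as a range. All 93 per arm are analysed, the SD is unchanged, and 20% of the active arm keeps only part of the effect (Noether):

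| Share of effect kept by the 20% | Average difference | Power |
|---|---|---|
| 100% | 15.00 | 80% |
| 75% | 14.25 | 76% |
| 50% | 13.50 | 72% |
| 0% | 12.00 | 62% |

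**The case against.** The strongest reply is that 71–72% is not the power of the primary analysis. The hypothesis is set in the FAS (Protocol 9.1), which needs one dose, a completed baseline and one valid post-randomization diary assessment (8.3). The endpoint uses whatever diary days exist (8.2). Most dropouts would therefore be analysed, and small losses cost little: 90 per arm still gives about 79%. In addition, study completion means attending through Visit 8 (5.7), whereas the endpoint period ends at Visit 7, so some subjects counted as dropouts could have complete primary data. All of this stands, and it is why 71–72% should be stated only as the power if about 150 contribute. It does not rescue the text: if the FAS makes dropout harmless, no adjustment was needed and none should be claimed.

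It is also fair that the documents do not give the timing of dropout, nor say whether the difference of 15 is an effect in completers or in all subjects. So dilution is possible but not shown. A subject who stops before about Day 28 would have mostly titration days, since titration takes the first 14; a later dropout would not.

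SAP 4.2 is not false in itself, because 93 analysed per arm does give 80%. It is incomplete. Finally, SAP 5.1 records that the study was halted after the two pediatric studies did not show efficacy, and SAP 6.1 plans only a descriptive summary of the primary endpoint. That limits the practical effect and rules out any reason to enrol more, but it does not make the statement correct.

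**Conclusion.** The point holds. The 186 is the sample size before dropout, presented as the size after it. No reading reconciles 80% power, 20% dropout and about 150 completers. On the plan's own assumptions, with normal data, power is about 80% if all 93 per arm are analysed at the full difference of 15, and about 71–72% if only about 75 per arm contribute. Power in the FAS lies at or below 80%, depending on how many dropouts have diary data and how much of the effect they show, which the documents do not settle. The per-protocol analysis (Protocol 9.2.3.3) requires completion of the Treatment Phase, so losses during that phase reduce it directly. The error is certain, and its practical effect is limited by the halt and the descriptive SAP.

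**What to change.** No further enrolment; restate the figure. In Protocol 9.3 and the Synopsis:

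- remove the inference that 186 is a total adjusted for dropout;
- state that 93 per arm is the number to be analysed in the FAS and includes no inflation for loss;
- state that 80% power applies only if all 186 enter the FAS at the assumed effect;
- state that power is about 71–72% if only about 150 subjects contribute.

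Add the same conditions to SAP 4.2, so that its 80% is not read as allowing for dropout.

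The cost is wording in three places and a less favourable power statement. No data collection, analysis or conduct changes.

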9.4 Exploratory Analyses

9.4.1 IA Diary Cross Validation

Cross-validation model will be generated based on the results from the IA diary validation in the 810P301 and 810P302 studies. The model will estimate the minimal clinical important change (MCIC) for improvement of IA behaviors in adolescents. The cross-validation plan and results will be provided in a separate report.

9.4.2 Pharmacokinetic

A population PK model will be developed for molindone using the nonlinear mixed-effects modeling program NONMEM. The structural model for molindone will incorporate data from

studies in which sampling was more intensive than in the present study. Results from the data analysis will be provided in a separate and stand-alone report.

9.4.3 Pharmacogenomic (PGx)

Genetic variations associated with CYP2D6 enzyme will be analyzed using the FAS population. Paired t-test will be used to compare the treatment groups, results will be summarized by treatment group using descriptive statistics. A stand-alone analysis and report will be generated.

9.5 Safety Analysis

Evaluation of safety will be performed for the safety population. Safety data that will be evaluated include concomitant medications, AEs, clinical laboratory results, vital signs, ECGs, and findings from the physical examinations. The occurrence of neurological side effects will be assessed by looking at any worsening in scores from Visit 3 to each subsequent visit for each of the Simpson-Angus scale, Barnes Akathisia scale, and AIMS. Suicidal ideation and suicidal behavior will be measured by C-SSRS.

All summary tables related to safety analyses will use the safety population.

9.5.1 Adverse Events

AEs will be classified into standardized medical terminology from the verbatim description (Investigator term) using the Medical Dictionary for Regulatory Activities (MedDRA). AEs will be summarized using discrete summaries at the subject and event level by system organ class and preferred term for each group of doses. Similarly, treatment-emergent AEs will be summarized by severity and relationship separately. Verbatim description and all MedDRA level terms, including the lower level terms, for all AEs will be contained in the subject data listings.

All AEs occurring throughout the study period will be recorded. Treatment-emergent AEs (TEAEs) will be collected starting after the first dose of study medication (after Visit 3) to the end of the study. These AEs include those that emerge during treatment or worsen in severity during treatment. These AEs will be tabulated, listed, and analyzed.

Separate TEAE incidence tables will be presented for the two treatment groups. The incidence rates for all SADRs will also be summarized as described for all TEAEs.

In addition, these same tables will be presented by treatment period (Titration, Maintenance, and combined Titration and Maintenance). For the combined Titration and Maintenance Periods, the incidence of TEAEs will also be presented by highest severity reported and the dose of SM at first occurrence. Listings (and tabular summaries, if warranted) of deaths, other SAEs, and other significant TEAEs, including TEAEs resulting in treatment discontinuation, will be provided.

9.5.2 **C-SSRS**

C-SSRS outcomes will be summarized using number and percent of subjects by categories for suicidal ideation only, suicidal behavior only and suicidality (ideation and behavior combined). The summary will be presented by treatment group. The proportion of subjects in each treatment group will be compared with the proportion of subjects in the placebo group using Fisher's exact test or Chi-square test as applicable if appropriate.

